6.2.4. Derived and Transformed Data

6.2.4.1. Primary Efficacy Variables

The primary efficacy endpoint is of symptomatic SMA Type 1 patients with biallelic SMN1 deletions and 2 copies of SMN2 without the genetic modifier (c.859G>C) that achieve the ability to sit without support for at least 10 seconds at any visit up to and including the 18 months of age visit. It is defined by the World Health Organization Multicentre Growth Reference Trial (WHO MGRS), confirmed by video recording, as a patient who sits up straight with head erect for at least 10 seconds; child does not use arms or hands to balance body or support position.

6.2.4.2. Supportive (Secondary and exploratory) Efficacy Variables

The secondary efficacy endpoint, event-free survival, is defined as avoidance of any one of the following events up to 14 months of age, whichever occurred first:

- Death, *or*
- Tracheostomy, *or*
- Noninvasive Ventilatory support ≥ 16 -hour per day *and* continuously ≥ 14 days

Usage data for patients using non-invasive ventilatory support will be extracted directly from the device (e.g., Trilogy 100, Trilogy 200, ResMed Stellar) on an SD card, or USB stick and transferred as an external dataset, if available. Average daily use of non-invasive ventilatory support at baseline and monthly be summarized from data recorded on an SD card or USB stick and submitted in a format that is evaluable. If a patient did not have a device with the capability to record usage data at baseline and was using non-invasive ventilatory support prior to screening, the daily usage will be documented in the source documentation. As a secondary analysis, the amount of ventilation support will be categorized into None, $>0-\leq 12$ hours, $>12-\leq 16$ hours, ≥ 16 or permanent ventilation. At each of the above time points, the count and percent of patients in each ventilation support category will be presented.

Supportive (exploratory) efficacy variables are as follows:

- CHOP-INTEND summary score: This is assessed by evaluating the Baseline CHOP-INTEND scores compared to each scheduled visit time points (see [Table 4](#)), collected from patient's CRF. A summary score is obtained by summing the individual best-side scores.
- Achievement of Selected Threshold Scores on CHOP-INTEND: clinically relevant threshold scores were determined for categorizing CHOP-INTEND summary scores: ≥ 40 , ≥ 50 , ≥ 58 .
- Bayley Scales of Infant and Toddler Development[®] version 3: Two domains of motor and adaptive behavior will be assessed from patient's CRF at scheduled visits (see [Table 1](#)) with both raw and scaled scores provided.
- Age at which independent sitting (for 10 seconds) is first achieved.
- Ability to remain independent of ventilator support, defined as requiring no daily ventilator support/usage at 18 months of age.
- Ability to thrive as defined by maintaining the ability to swallow and to maintain weight ($>$ third percentile based on WHO CGRS without need of gastrostomy or other mechanical or non-oral nutritional support at 18 months of age)

6.2.4.3. First observed date of video confirmed milestone

All videos, either from study visits or caregiver provided home videos which meet WHO and BSID criteria for items on the developmental milestone checklist will be provided to an independent central reviewer for unbiased assessment of developmental milestone achievement. The independent central reviewer will document whether the video displays evidence of having achieved developmental milestone.

The date in which a Developmental Milestone is first observed and recorded on video, clinic or home video is entered into [REDACTED]. In the event that the Central Reviewer does not confirm the milestone, video evidence will be provided from subsequent clinic visit or home video footage until confirmation is received. The earliest date of video recording which is confirmed by central review is considered the date of developmental milestone achievement.

6.2.4.4. Safety Variables

The safety endpoint is defined as the patient meeting the following criteria:

- Any AE
- Any serious AE
- Any AE related to study product
- Any AE with CTCAE Grade \geq Grade 3

This will be collected at all scheduled visits (see [Table 1](#)) from patient's CRF. Adverse Event collection methods for the observational natural history cohort were not consistent with rigorous Adverse Event collection methods demonstrated in the context of an interventional clinical research study; therefore, only descriptive statistics will be presented.

6.3. Handling Missing Data

All patients in the ITT analysis set will be included in the primary efficacy analysis for a given endpoint provided there are non-missing baseline values. If a patient misses a regularly scheduled visit, every attempt will be made to reschedule a visit within that visit window to obtain evaluations or tests.

For the primary endpoint (the ability to sit without support for 10 seconds at up to 18 months of age) collected during the study, only when a patient demonstrates the ability in a video recorded at a visit or at home and confirmed by a central reviewer, a “Yes/True” value will be reported in the MMI report. A missing value of the primary endpoint of a patient means the patient does not achieve the ability of the milestone. No imputation is necessary.

For secondary efficacy endpoint, only when a patient met the survival criteria, the date of death or permanent ventilation will be reported through [REDACTED]. Patients who terminate the study prior to reaching 14 months of age for any reason will be considered treatment failures (event). Patients who terminate the study after 14 months of age but are still event-free surviving at the time of termination will be censored.

The following strategies will be implemented for different efficacy endpoints

- Central reviewed developmental milestone. No imputation will be implemented
- CHOP-INTEND score. No sub item score will be imputed. If the missing total score is due to “Can not test (CNT)”, no imputation will be implemented. Otherwise, last observation carried forward (LOCF) will be applied to impute the missing values.
- Bayley Scales of Infant and Toddler Development. LOCF will be implemented to impute the missing values
- Swallowing, feeding support and ventilation support. No imputation will be implemented.

In addition, missing values for safety endpoints, including but not limited to AE, lab values, will not be imputed. For local lab, missing units or normal ranges will be reviewed by the medical team. If those missing information needs be imputed for selected lab tests, the imputed information will be captured in the Note to File (NTF). The following tables provides the most conservative way to impute the date of event, if a missing date observed and not able to be fixed on the source.

Table 2: Rules of Date Imputation: Pre-Dose Data

| Partial Missing Start or Stop Date | Imputed Start Date | Imputed Stop Date |
|--|--|-----------------------------------|
| Missing month and day, but the year is present | January 1 of that year or dose date if the year is the same as the year of dose date | December 31 of that year |
| Missing day, but year and month are present | First day of that month or dose date if the year and month are the same as the year and month of dose date | Last day of that month |
| Missing month, but year and day are present | Missing month imputed as January | Missing month imputed as December |

Table 3: Rules of Date Imputation: Post-Dose Data

| Partial Missing Start or Stop Date | Imputed Start Date | Imputed Stop Date |
|--|--|-----------------------------------|
| Missing month and day, but the year is present | Date of dose | December 31 of that year |
| Missing day, but year and month are present | First day of that month or dose date if the year and month are the same as the year and month of dose date | Last day of that month |
| Missing month, but year and day are present | Date of dose | Missing month imputed as December |

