3.5. Study Design

This is a Phase 3, open-label, single-arm, single-dose trial of AVXS-101 (gene replacement therapy) in patients with SMA Type 1 with one or two copies of *SMN2*. Up to 30 patients < 6 months (< 180 days) of age at the time of gene replacement therapy (Day 1) will be enrolled.

The trial includes 3 trial periods: screening, gene replacement therapy, and follow-up (**Error! Reference source not found.1**). During the screening period (Days –30 to –2), patients whose parent(s)/legal guardian(s) provide informed consent will undergo screening procedures to determine eligibility for trial enrollment. Patients who meet the entry criteria will enter the in-patient gene replacement therapy period (Day –1 to Day 3). On Day –1, patients will be admitted to the hospital for pre-treatment baseline procedures. On Day 1, patients will receive a one-time intravenous (IV) infusion of the equivalent of AVXS-101 cohort 2 dose received in the AVXS-101-CL-101 trial over approximately 30-60 minutes, dependent upon required total volume, and will undergo in-patient safety monitoring over the next 48 hours. Patients may be discharged 48 hours after gene replacement therapy, based on Investigator judgment. During the outpatient follow-up period (Days 4 to End of Trial at 18 months of age), patients will return at regularly scheduled intervals for efficacy and safety assessments until the patient reaches 18 months of age. Any missed visit should be rescheduled as soon as possible, but within the visit windows specified in the schedule of assessments.

All post-treatment visits will be relative to the date on which gene replacement therapy is administered, until the patient is 14 months of age, after which will be relative to the patient's date of birth. For the 14 and 18 months of age visits, the patient will return within 0 to 14 days after the date on which the patient reaches 14 and 18 months of age, respectively. The 18 months of age visit will also serve as the End of Trial visit. After the End of Trial visit, eligible patients will be asked to participate in the long-term follow-up trial.

Figure 1: Study Design Schematic

Note: After the End of Trial visit at 18 months of age or at the time of early discontinuation patients will be invited to participate in a long term follow up study conducted under a separate protocol.

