6.4.1. Study Day Based Visit Windows

For efficacy analysis, the time windows specified in [Table 4](#) describe how efficacy data will be assigned to protocol-specified time points, as displayed in the Schedule of Assessments in [SAP Section 3.5.1](#). All time points and corresponding time windows are defined based on Dosing Date.

If more than one efficacy observation for a specific assessment is included in a time window, the assessment closer to the nominal time will be used. If there are two efficacy observations equally distant to the nominal time, the latest one will be used in analyses. Any efficacy assessments occurring outside the analysis windows will be considered an assessment of an unscheduled visit.

Table 4: Study Day Based Visit Window

| Scheduled Visit | Nominal Days (Study Day) | Acceptable Analysis Window in Study Days (Min Day – Max Day) |
|--|--------------------------|--|
| Baseline | - | <1 |
| Month 1 | 30 | 1 to 44 |
| Month 2 | 60 | 45 to 74 |
| Month 3 | 90 | 75 to 104 |
| Month 4 | 120 | 105 to 134 |
| Month 5 | 150 | 135 to 164 |
| Month 6 | 180 | 165 to 194 |
| Month 7 | 210 | 195 to 224 |
| Month 8 | 240 | 225 to 254 |
| Month 9 | 270 | 255 to 284 |
| Month 10 | 300 | 285 to 314 |
| Month 11 | 330 | 315 to 344 |
| Month 12 | 360 | 345 to 374 |
| Month 13 | 390 | 375 to 404 |
| Month 14 | 420 | 405 to 434 |
| Month 15 | 450 | 435 to 464 |
| Month 16 | 480 | 465 to 494 |
| Month 17 | 510 | 495 to 539 |
| Month 18 | 540 | 540 to 569 |
| Month K | K*30 | K*30 to (K+1)*30-1 |
| Final Treatment Visit and 14 Months of Age Analysis Window | | 0 to ≤14 days after patient reaches 14 months of age (420-434 days of age) visit window; 0 to ≤14 days after patient reaches 18 months of age (540 days of age) visit window |

*Depending on age at time of dosing, patients will complete varying number of visits. The patient must complete a visit within 2 weeks after reaching 14 months of age; subsequent visits will be scheduled from that visit date. The patient must also complete the final study visit within 2 weeks after reaching 18 months of age.

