8.3.14. Proportion of Patients that Achieve Ability to Walk Alone

The ability to walk alone is defined by WHO development milestones and will be based upon the maximum function achieved at any time point up to 18 months of age.

The numbers and percentages of patients who achieve ability to walk alone by the final visit will be presented by overall and by subgroups, including subgroups, age at the time of treatment (≤ 4 months, >4 months). The observed proportion achieving ability to walk alone during the observation period will be compared to zero using a 1-sided Exact Binomial Test, along with the corresponding 97.5% confidence intervals. To make computation of the p-value possible, the value of 0.1% will be used in place of a literal zero.

8.3.15. Improvement of Raw Score and Scaled Score using Bayley Scales of Infant and Toddler Development (Version 3), Fine and Gross Motor Function Subtests

Descriptive statistics for change from baseline in Fine and Gross motor function raw and scaled scores will be presented at each Study Day based visit, including mean, standard deviation, median, minimum, and maximum values.

Descriptive statistics for change from baseline in Fine and Gross motor function raw and scaled scores will also be presented at each Age Based visit, including mean, standard deviation, median, minimum, and maximum values.

The change from baseline of Bayley raw score to maximum score at any visit will be presented at by overall. An ANCOVA model with subgroup variable, as the factor and baseline Bayley score as a covariate, will be used to evaluate the comparability of the maximum change of Bayley score between subgroups.

The change from baseline will be analyzed by using mixed model with repeated measurement (MMRM). The model will include the change from baseline as the dependent variable, and fixed effects of subgroup, visit, and a covariate of baseline, age at baseline, and interactions of subgroup*visit, baseline*visit. A Toeplitz covariance structure will be assumed initially to model the within-patient errors; however, if the covariance structure results in non-convergence, the structure of compound symmetry will be used. The mean change from baseline (%), least squares (LS) means, differences between LS means, a 95% 2-sided CLs for each difference and the p-values from model effects will be reported for each scheduled visit through Month 18.

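### The exploratory Bayley MMRM promises subgroup estimates through Month 18, but children dosed after day 120 have no observed value at study-day Months 16–18, and the model adjusts the age subgroup for age

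*SAP*

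**What the plan says.** SAP 8.3.15 models Bayley change from baseline with "fixed effects of subgroup, visit, and a covariate of baseline, age at baseline, and interactions of" subgroup by visit and baseline by visit. On covariance it says "A Toeplitz covariance structure will be assumed initially to model the within-patient errors", with compound symmetry as the fallback. The model-based means, subgroup differences, confidence limits and p-values "will be reported for each scheduled visit through Month 18". The only subgroups that SAP 6.7 defines, and it names the modelling for them, are dosing at 120 days of age or younger and dosing after 120 days.

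SAP 6.3 states the Bayley missing-data rule in one line: "LOCF will be implemented to impute the missing values". The same section opens with missed visits: "If a patient misses a regularly scheduled visit, every attempt will be made to reschedule a visit within that visit window".

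SAP 6.4 gives two analysis schedules, by study day (Table 4) and by age (Table 5). Of Table 4, SAP 6.4.1 says "All time points and corresponding time windows are defined based on Dosing Date", and its footnote adds "Depending on age at time of dosing, patients will complete varying number of visits". SAP 6.2.3 closes the Bayley final value at 570 days of age. The protocol's visit window for 18 months of age closes 14 days after day 540, which is day 554.

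**The concern.** Follow-up ends at a fixed age, while Table 4 counts from dosing. The later a child is dosed, the fewer Table 4 months that child can reach, and the subgroup variable is age at dosing itself. The late subgroup-by-visit cells are therefore empty by design for one subgroup. They are not missing through dropout.

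The SAP promises estimates and p-values for those cells without saying what fills them. One programmer could return non-estimable cells. Another, applying 6.3 literally, could return estimates in which every value in the later-dosed subgroup is carried forward. In a growing infant whose score is rising, a carried value is too low, and it is carried furthest in the children dosed latest, so the error favours earlier dosing.

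The second matter is the covariate list. Subgroup is a cut of age at dosing, and the model also adjusts for continuous age. The subgroup coefficient then measures a step at 120 days over and above a linear age trend, not how children dosed later differ from children dosed earlier.

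**Working it through.** **Inputs.** Dosing before 180 days of age (SAP 5.2), so at most day 179. Subgroup cut at 120 days (6.7). Study day = event date − dosing date + 1 (1.2). Final visit at 540 to 554 days of age, or 570 at the SAP limit (6.2.3). Table 4 windows: Month 12 is study days 345–374, Month 13 375–404, Month 14 405–434, Month 15 435–464, Month 16 465–494, Month 17 495–539, Month 18 540–569.

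**Formula.** Last study day = age at final visit − age at dosing + 1.

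**The plan's own figure first.** The SAP's design schematic note gives participation of about 12 to 18 months. Dosed on day 1: 540 − 1 + 1 = 540 days, or 18.0 months of 30 days. Dosed on day 179: 540 − 179 + 1 = 362 days, or 12.07 months. Both agree.

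**Last study day reached**

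| Age at dosing (days) | Final visit at 540 | at 554 | at 570 |
|---|---|---|---|
| 121 | 420 | 434 | 450 |
| 179 | 362 | 376 | 392 |

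Day 121 is the youngest dosing age in the later subgroup, so its row is the maximum. Month 15 starts at 435 and Month 16 at 465. The subgroup therefore has no value at Months 16–18 under any of the three limits, and none at Month 15 if seen by day 554. A child dosed on day 121 would have to be 121 + 540 − 1 = 660 days old to enter the Month 18 window.

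The younger subgroup is thin there too. Reaching study day 540 needs dosing by day 15 for a final visit at 554 days (554 − 540 + 1), or by day 31 at 570.

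**How coverage falls off.** Assume dosing ages uniform over days 121–179. Over the three limits, the share of this subgroup with no own value is 0% at Month 12, 0–22% at Month 13, 22–73% at Month 14, 73–100% at Month 15 and 100% at Months 16–18.

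**If LOCF fills the gap.** Values are carried 90 days (540 − 450) to 178 days (540 − 362) to nominal day 540. To size the effect, assume a gain of 1 point per month, no true age effect, and dosing ages uniform from a first age of day 1, 30, 60 or 90 up to day 179. The response is min(30m, last study day)/30 at month m. A generalised least squares fit with visit, subgroup by visit and one age slope (baseline terms left out) gives these false differences, later minus earlier dosing:

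- Month 18, independence or compound symmetry: −1.1 to −2.6 points.
- Month 18, AR(1) with correlation 0.9 to 0.95: −0.9 to −2.1 points.
- Months 1–12: +0.3 to +0.5 and +0.6 to +1.2 respectively, because the single age slope takes up part of the late deficit and pushes the early contrasts the other way.
- Raw Month 18 contrast, without the model: −1.5 to −3.0 points.

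**If the age schedule (Table 5) were used.** The first post-dose Bayley is at Day 30, at age 121 + 29 = 150 to 179 + 29 = 208 days. The 5-month window starts at 150 days. Windows below about 5 months are then empty or nearly so for this subgroup, with no post-dose value to carry. The exception is a child dosed on day 121 or 122 and seen on study day 28, two days early: age 148 or 149, inside the 4-month window (120–149).

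**Two age terms.** With the same assumed dosing ages, the correlation between age at dosing and the subgroup indicator is 0.81 to 0.87, and the variance inflation factor, 1/(1 − r²), is 3.0 to 4.0. Suppose each month of later dosing costs 1 point at every visit. The mean dosing ages of the subgroups differ by 1.5 to 3.0 months, so the true contrast is −1.5 to −3.0 points. That effect is an exact multiple of the age column, so the age slope absorbs it and the fitted subgroup difference is 0.

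**The case against.** The strongest reply is that the SAP can be read so that nothing false is produced. Section 6.3 speaks of missing a regularly scheduled visit, and the Table 4 footnote accepts that visit numbers vary with age at dosing. Section 6.4.1 groups efficacy data collected after the 18-months-of-age visit separately, and 8.3 bases hypothesis testing on data collected up to 18 months of age. For a child dosed after day 120, Months 16–18 lie beyond that point. This makes it the more natural reading that LOCF stops at the child's own last visit, and the cost is then visible blanks rather than a biased result. That stands, but none of these sentences mentions imputation, and the estimates that 8.3.15 promises still cannot be delivered. The output specifications are kept in separate TLF documentation and may settle the rule. The SAP does not.

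Two stronger readings should be set aside.

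- A reader might count three visit schedules, because visits run "relative to the date on which gene replacement therapy is administered, until the patient is 14 months of age" and by birth date afterwards, and conclude that dosing Months 11–13 are also empty. That is how visits are booked. SAP 6.4 applies two analysis schedules, and Table 4 assigns whatever was observed by study day. Scheduled visit and Month 18 are also Table 4's own labels, so the study-day schedule is the likely intent.
- A reader might infer that the earlier-versus-later contrast is lost altogether. The ANCOVA of maximum Bayley change in the same section uses subgroup and baseline without age, so that contrast is available on the protocol's own Bayley endpoint.

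It is also fair to say that the bias figures rest on a gain and an age distribution that the documents do not give, and on simple covariance forms in place of a fitted Toeplitz.

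**Conclusion.** The point holds and is minor. The coverage gap follows from the documents alone: on Table 4 the subgroup dosed after day 120 has no observed Bayley value at Months 16–18, nor at Month 15 with a final visit by day 554, yet estimates and p-values are promised through Month 18. Those cells are non-estimable on the more natural reading of LOCF and wholly carried on the literal one.

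The false Month 18 difference of about −0.9 to −2.6 points applies only on the literal reading, and only under the assumed 1 point per month, uniform dosing ages, no true age effect and a simplified model. It shows direction and rough scale and does not predict the trial's result. The age-term problem does not depend on LOCF. Its correlation of 0.81 to 0.87 does depend on the assumed dosing ages and on age at baseline meaning age at dosing.

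A reader might take this as a threat to the efficacy conclusion. It is not one. The model is exploratory and outside the testing hierarchy in SAP 8.4. The primary and secondary results and the protocol's Bayley change-to-maximum endpoint do not depend on it.

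**What to change.** - **SAP 6.3:** exclude the Bayley MMRM from LOCF. Use observed data only, with nothing entered after the child's own end-of-trial visit.
- **SAP 8.3.15, schedule:** state that the model uses the Table 4 study-day schedule, and report model estimates only at visits where both subgroups have observed data. That means through Month 12 if every child is to be able to contribute, or Month 14 at most under the 554-day window. With 30 children and the dosing ages assumed above, about 3 (16/179 × 30 = 2.7) to 10 (30/90 × 30) would be later-dosed children with a Month 14 value, so a minimum number per subgroup should be stated.
- **SAP 8.3.15, covariates:** drop continuous age at baseline from the subgroup model, as the ANCOVA in that section does.

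The cost is a few sentences and a simpler program. The downside is that the sparse late visits have no model estimates. They stay in the descriptive tables.

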| TEAE | Treatment-emergent Adverse Event = any adverse event whose onset (or worsening of an existing AE) occurred on or post day of gene therapy infusion. |
| Vector genome | The human SMN cDNA sequence, corresponding to the mature mRNA, cloned into the self-complementary AAV vector plasmid. |

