5.2. Intent-to-Treat (ITT) Population

The ITT population will consist of symptomatic patients with bi-allelic deletion of *SMN1* (exon 7/8 common homozygous deletions) and 2 copies of *SMN2* without the known gene modifier mutation (c.859G>C) who receive an IV infusion of AVXS-101 at less than 180 days of age.

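### The partial-date rules in SAP 6.3 give start dates that contradict the recorded year or day, precede birth, or move pre-dose items onto the dose date

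*SAP*

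**What the plan says.** SAP 6.3 introduces its date rules with "The following tables provides the most conservative way to impute the date of event". They apply where a date is partly missing and cannot be put right at source. Table 2 covers pre-dose data and Table 3 post-dose data. The start-date rules are:

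- Table 3, year only: "Missing month and day, but the year is present | Date of dose".
- Table 3, year and day without month: "Missing month, but year and day are present | Date of dose".
- Table 2, year only: "January 1 of that year or dose date if the year is the same as the year of dose date".
- Table 2, year and day without month: "Missing month, but year and day are present | Missing month imputed as January".
- Both tables, year and month without day: "First day of that month or dose date if the year and month are the same as the year and month of dose date".

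No row mentions the birth date or a known stop date, and nothing in Table 2 keeps an imputed start before dosing.

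Four other provisions bear on these dates:

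- The glossary (SAP 1.2) counts an adverse event as treatment-emergent if its onset or worsening "occurred on or post day of gene therapy infusion".
- SAP 7.4 calls a medication prior if it was taken before the infusion date. It calls it concomitant if it continued past the infusion or started on or after that date.
- SAP 10.3.1 presumes that an adverse event with an incomplete onset date is treatment-emergent, unless other evidence shows that it was not.
- SAP 5.2 defines the ITT population as patients "who receive an IV infusion of AVXS-101 at less than 180 days of age". Protocol 8.1 sets the same age limit for every enrolled patient.

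**The concern.** An imputed date should agree with whatever part of the date was actually recorded. Two of the three start rows in Table 3 discard a known year, and one of those also discards a known day. Table 2 is written as if for adults: in infants under 180 days old, going back to January can easily pass the date of birth. Its same-year and same-month clauses then do the opposite and push an item already known to be pre-dose forward onto the dose date.

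The stakes are the credibility of safety listings and study days, and the line between prior and concomitant medication. A late event shown as Day 1, or a drug started before the patient was born, is the kind of record that data reviewers and inspectors query.

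**Working it through.** The plan gives no figure to reproduce, so the check applies the table text literally.

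**Inputs.** Age at dosing is under 180 days (SAP 5.2, Protocol 8.1). Follow-up runs to 540 days of age plus up to 14 days, so 540 + 14 = 554 (SAP 6.4.1). Study Day = event date − dose date + 1 (SAP 1.2). The illustrative patient is my assumption: born 20 October 2018 and dosed 15 February 2019, at age 118 + 1 = 119 days.

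**Earliest possible Study Day for a 2020 onset.** 15 February 2019 to 1 January 2020 is 320 days, so 320 + 1 = Study Day 321.

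| Recorded start | Table gives | Conflict | Earliest date that fits |
|---|---|---|---|
| Post-dose: year 2020 | 15 Feb 2019 (Day 1) | wrong year | 1 Jan 2020 (Day 321) |
| Post-dose: day 10, 2020 | 15 Feb 2019 (Day 1) | wrong year and day | 10 Jan 2020 (321 + 9 = Day 330) |
| Post-dose: day 20, 2019 | 15 Feb 2019 (Day 1) | wrong day | 20 Feb 2019 (5 + 1 = Day 6) |
| Post-dose: March 2020 | 1 Mar 2020 (321 + 60 = Day 381) | none | the same |
| Pre-dose: year 2018 | 1 Jan 2018 | 292 days before birth | 20 Oct 2018 |
| Pre-dose: day 25, 2018 | 25 Jan 2018 | 268 days before birth | 25 Oct 2018 |
| Pre-dose: October 2018 | 1 Oct 2018 | 19 days before birth | 20 Oct 2018 |
| Pre-dose: year 2019, stop 28 Jan 2019 | 15 Feb 2019 | on the dose date, 18 days after the stop | 1 Jan 2019 |
| Pre-dose: February 2019 | 15 Feb 2019 | on the dose date | 1 Feb 2019 |

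**Why the prior-year case always fails.** If dosing falls in year Y, 1 January of Y − 1 is at least 365 days earlier. Birth is fewer than 180 days before dosing. The imputed date therefore precedes birth by more than 365 − 180 = 185 days, whoever the patient is.

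**How general the pattern is.** I ran the rules over a grid of dose dates across 2019, ages at dosing from 1 to 179 days, and true event dates from birth to 554 days of age. The figures are shares of records with the given missing pattern, under an assumed even spread of dates. They are not forecasts of how often partial dates will occur.

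- Post-dose, year only: 60.5% contradict the recorded year, by up to 552 days.
- Post-dose, month missing: 98.3% contradict the recorded year or day.
- Post-dose, day missing: 0% contradict.
- Pre-dose, year only: 83.3% land on the dose date and 16.7% before birth, so none is left usable.
- Pre-dose, month missing: 79.4% fall before birth and none on or after the dose date.
- Pre-dose, day missing: 15.6% land on the dose date and 14.6% before birth.

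**What follows downstream.** A medicine recorded as started in the dosing year and stopped before the infusion gets the dose date as its start. Read from its dates, it was no longer taken before infusion, so it drops out of the prior group in SAP 7.4 and its start falls after its stop. A pre-dose adverse event moved to the dose date meets the glossary wording for treatment emergence. A post-dose event is treatment-emergent whether it sits on Day 1 or Day 321, so Table 3 cannot change that status.

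**The case against.** The strongest reply is that leaning early on starts and towards treatment emergence is a deliberate, cautious choice for safety data, and that little depends on the result. Much of this stands.

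- A reader might infer that pre-existing conditions will be counted as treatment-emergent events. The documents do not support that. SAP 10.3.1 lets evidence of pre-dose onset override the presumption, and an event handled under Table 2 is already known to be pre-dose. Medical history is summarised without dates (SAP 7.3). What remains is a conflict between the glossary wording and the imputed date.
- A reader might infer that adverse event tables on onset or duration will be distorted. SAP 10.3.2 plans counts by system organ class, preferred term, grade and relationship; none uses onset day or duration.
- A reader might extend the rules to dates of death or permanent ventilation, because the introductory sentence speaks of event dates. That sentence stands in the paragraph on safety data, and nothing in the SAP applies the tables to the survival analysis.
- An onset on the dose date is a possible calendar date. It is strictly impossible only when a known stop precedes it; otherwise it contradicts the item's pre-dose status.
- The reach is narrow. Adverse events are collected from consent (Protocol 13.1.1) and screening starts at Day −30 (Protocol 7.1). A pre-dose event from the previous calendar year therefore generally needs dosing in about January. Pre-birth dates would arise mainly for medication starts and medical history.

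The appeal to caution does not rescue the rules themselves. Discarding a recorded year adds no protection for an event that is treatment-emergent anyway. Nor is it cautious to place a start before birth or after a known stop.

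**Conclusion.** The point holds: these start-date rules are wrong as written, with minor consequences. Two of the three start rows in Table 3 contradict recorded data; its missing-day row is sound. In Table 2, a year-only start always ends up on the dose date or before birth. The missing-month row can fall before birth, and the missing-day row can fall before birth or on the dose date.

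A single date can be badly displaced: at least 320 days in the 2020 onset example, and 292 days before birth in the 2018 one. The overall effect is confined to safety listings, study days and prior/concomitant classification. The primary endpoint is unaffected, because centrally reviewed milestones are not imputed (SAP 6.3), and post-dose treatment-emergent counts are unaffected.

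This rests on a literal reading of the tables and on the assumption that few partial dates will survive source correction. The documents do not give that number.

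**What to change.** Replace the start-date columns of both tables with one principle each.

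- **Post-dose starts:** the earliest date that agrees with every recorded component and is on or after the dose date. The dosing year needs the same check. Reverting to the dose date whenever the year matches would still contradict a recorded day, as in the day 20, 2019 example.
- **Pre-dose starts:** the earliest date that agrees with the recorded components, is not before birth, is before the dose date, and is not after a known stop date.
- If no date meets the conditions, the record is inconsistent and should be queried, not imputed.

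Do not add a general cap that sets pre-dose stop dates to the day before dosing. A medicine started before dosing and stopped on an unknown later date may have continued past the infusion, and a cap would hide that exposure from the concomitant group. Cap a stop only where the record shows that the item ended before dosing.

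The cost is two table edits and minor programming. No new data are needed and no efficacy analysis changes.
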